### Research Activity

Check all that apply and complete the appropriate sections as instructed.

1.  **Drug & Device:** Drugs for which an investigational new drug application is not required. Device for which (i) an investigational device exemption application is not required; or the medical device is cleared/approved for marketing and being used in accordance with its cleared/approved labeling. (Specify in the Methods section)
2.  **Blood:** Collection of blood samples by finger stick, heel stick, ear stick, or venipuncture.
3.  **Biological specimens other than blood:** Prospective collection of human biological specimens by noninvasive means that may include: urine, sweat, saliva, buccal scraping, oral/anal/vaginal swab, sputum, hair and nail clippings, etc.
4.  **Tests & Procedures:** Collection of data through noninvasive tests and procedures routinely employed in clinical practice that may include: MRI, surface EEG, echo, ultrasound, moderate exercise, muscular strength & flexibility testing, biometrics, cognition testing, eye exam, etc. (Specify in the Methods section)

5.  **Data** (medical record, images, or specimens): Research involving use of existing and/or prospectively collected data.
  6.  **Digital Record:** Collection of electronic data from voice, video, digital, or image recording. (Specify in the Methods section)
  7.  **Survey, Interview, Focus Group:** Research on individual or group characteristics or behavior, survey, interview, oral history, focus group, program evaluation, etc. (Specify in the Methods section)
- NIH has issued a *Certificate of Confidentiality (COC)*. *When checked, provide the institution and investigator named on the COC and explain why one was requested.* \_\_\_\_\_

### HIPAA Identifiers and Protected Health Information (PHI)

Protected health information is medical data that can be linked to the subject directly or through a combination of indirect identifiers.

Recording identifiers (including a code) during the conduct of the study allows you to return to the medical record or data source to delete duplicate subjects, check a missing or questionable entry, add new data points, etc. De-identified data is medical information that has been stripped of **all** HIPAA identifiers so that it cannot be linked back to the subject. De-identified data is **rarely** used in the conduct of a research study involving a chart review.

**Review the list of subject identifiers below and, if applicable, check the box next to each HIPAA identifier being recorded at the time of data collection or abstraction.** Identifiers apply to any subject enrolled in the study including Mayo Clinic staff, patients and their relatives and household members.

**Internal** refers to the subject's identifier that will be recorded at Mayo Clinic by the study staff.

**External** refers to the subject's identifier that will be shared outside of Mayo Clinic.

Check all that apply:	INTERNAL	EXTERNAL
Name	X	
Mayo Clinic medical record or patient registration number, lab accession, specimen or radiologic image number	X	
Subject ID, subject code or any other person-specific unique identifying number, characteristic or code that can link the subject to their medical data		
Dates: All elements of dates [month, day, and year] directly related to an individual, their birth date, date of death, date of diagnosis, etc. Note: Recording a year only is not a unique identifier.	X	
Social Security number		
Medical device identifiers and serial numbers		
Biometric identifiers, including finger and voice prints, full face photographic images and any comparable images		
Web Universal Resource Locators (URLs), Internet Protocol (IP) address numbers, email address	X	
Street address, city, county, precinct, zip code, and their equivalent geocodes		
Phone or fax numbers		
Account, member, certificate or professional license numbers, health beneficiary numbers		
Vehicle identifiers and serial numbers, including license plate numbers		
Check 'None' when none of the identifiers listed above will be recorded, maintained, or shared during the conduct of this study. (exempt category 4)	 None	 None

## Data Analysis

*Power analyses and study endpoints are not required for minimal risk research, pilot or feasibility studies.*

No statistical information. *If checked, please explain:*

### Statistical Considerations

#### Randomization

Subjects will be randomized into one of two study groups: mepivacaine or low-dose bupivacaine. In order to ensure balance on the subject demographics between the two study groups, the subjects will be stratified on procedure (TKA vs THA), gender, age group ( $\geq 70$  vs.  $< 70$ ) and BMI ( $\geq 32$  vs.  $< 32$ ). Within each stratum, subjects will be assigned to either of the two study groups using a computerized dynamic allocation program housed in an online application developed by personnel in the Division of Biomedical Statistics and Informatics. Using dynamic allocation will ensure that the subject allocation will remain balanced on the stratification factors and the study group assignment throughout the entire subject accrual phase.

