#### Sample Size

An a priori power analysis was conducted using internal data from Mayo patients undergoing primary TJA with mepivacaine (N=6) and low-dose bupivacaine (N=5). In these two cohorts, standard deviations of the time to return of full lower extremity motor function were 37 minutes and 89 minutes, respectively, yielding a pooled estimate of the common standard deviation equal to 65.6 minutes. Assuming that similar variability will be observed in the proposed study, a sample of 150 subjects per group (300 total) will be required to have 80% power to detect a difference of at least 30 minutes in mean time to return to full lower extremity motor function between the 2 study groups. With the typical volume of the participating surgical group, we anticipate enrollment will be complete within 3 months.

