#### Analysis

[name] will lead the data analysis effort. All pre- and post-operative data will be entered by the study coordinator into standardized Excel Spreadsheets and RedCap forms as appropriate. The data will primarily be collected by the lead Study Coordinator and checked for accuracy and completeness by [name]. All outcomes will be reported descriptively using appropriate summary statistics, including 95% confidence intervals, where appropriate. Because this is a prospective, randomized trial, no formal between-group comparisons of baseline covariates will be performed. The primary study outcome will be time to return of full lower extremity motor function. Secondly, we will assess a variety of both continuous and categorical outcomes between groups including pain scores, opioid consumption, urinary retention, transient neurologic symptoms, length of PACU stay, length of hospital stay, time to participation in physical therapy and walking distance with physical therapy. Outcomes measured on a continuous scale, including time to full lower extremity motor function, length of PACU stay and hospital stay, time to participation in physical therapy, and walking distance will be compared between the 2 study groups using two-sample t-tests if the data are sufficiently normally distributed; otherwise non-parametric Wilcoxon rank sum tests will be used. Ordinal variables such as pain scores will be analyzed using non-parametric Wilcoxon rank sum tests. Binary and nominal categorical outcomes will be compared between the study groups using chi-square tests or Fisher's exact tests, if low expected cell counts are observed. All statistical tests will be two-sided and the threshold of statistical significance will be set at  $\alpha = 0.05$ .

While it is expected that the study enrollment will be complete in approximately 4 to 6 months, one interim analysis will be performed at 2 months, or once half the subjects have been enrolled, whichever comes first. The Lan-DeMets alpha spending function with O'Brien-Fleming type boundaries will be utilized to maintain the overall type 1 error rate at  $\alpha=0.05$ , regardless of the timing of the analysis.

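### Allocation is balanced on procedure, gender, age and BMI but every planned comparison is unadjusted: valid, but conservative with over-wide intervals if those factors predict outcome

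*Combined protocol and SAP*

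**What the plan says.** **Allocation.** Under Statistical Considerations, the Randomization section says "the subjects will be stratified on procedure (TKA vs THA), gender, age group" (cut at 70) and BMI (cut at 32). It adds: "Using dynamic allocation will ensure that the subject allocation will remain balanced on the stratification factors". The particular algorithm is not named. The stated purpose is demographic balance; the section does not claim that the factors predict any outcome.

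**Analysis.** Continuous outcomes, including the primary time to full motor function, are compared "using two-sample t-tests if the data are sufficiently normally distributed; otherwise non-parametric Wilcoxon rank sum tests will be used". For ordinal outcomes: "Ordinal variables such as pain scores will be analyzed using non-parametric Wilcoxon rank sum tests". For the rest: "Binary and nominal categorical outcomes will be compared between the study groups using chi-square tests", or Fisher's exact test when expected counts are low. Results are described with "appropriate summary statistics, including 95% confidence intervals, where appropriate". No regression model, stratified test, re-randomisation test or adjusted interval appears. Baseline covariates are mentioned only to say that "no formal between-group comparisons of baseline covariates will be performed".

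**Sample size.** The Sample Size section combines two small internal cohorts, "yielding a pooled estimate of the common standard deviation equal to 65.6 minutes", and sets 150 per group with a target difference of 30 minutes.

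**The concern.** When allocation forces balance on a factor that predicts the outcome, the two arms can no longer differ by chance on that factor. The true sampling variation of the arm difference shrinks. An unadjusted test does not know this: its standard error still counts the factor's share of the outcome variance as noise. The test then rejects less often than its nominal level under the null, and the interval covers more often than 95%.

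What is at stake is efficiency and accurate reporting. The balance built into the design would not be credited in the analysis, and intervals labelled 95% would be wider than needed. This matters most for the secondary outcomes (pain, opioid use, length of stay, therapy measures), for which the plan gives no power calculation.

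**Working it through.** **Inputs from the documents.** SD 65.6 min, 150 per group, difference 30 min (Sample Size); two-sided 5% level (Analysis); four binary balancing factors (Randomization).

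**Assumed input.** R², the share of outcome variance explained by the four factors. The documents give none, so a range of 0 to 30% is shown.

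**The plan's own figures.** From the rounded cohort SDs, the pooled SD is √[(5×37² + 4×89²)/9] = √(38,529/9) = 65.4 min. The stated 65.6 is within rounding. The stated 80% power does not reproduce: with these inputs 76 per group give 80%, and 150 per group give about 98%. That is a separate matter. It bears here only on the power columns, as noted under the objection.

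**Formulas.**
- Unadjusted SE = 65.6 × √(2/150) = 7.57 min; half-width = 1.96 × 7.57 = 14.8 min.
- With balance, true SE = 7.57 × √(1 − R²). An adjusted analysis estimates this; the unadjusted one keeps 7.57.
- True size of the unadjusted test = 2 × [1 − Φ(1.96/√(1 − R²))].
- Power, unadjusted = Φ[(30 − 1.96 × 7.57)/(7.57 × √(1 − R²))].
- Power, adjusted = Φ[30/(7.57 × √(1 − R²)) − 1.96].

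**Example, R² = 20%.** True SE = 7.57 × 0.894 = 6.77. Adjusted half-width = 1.96 × 6.77 = 13.3. Size = 2 × [1 − Φ(2.19)] = 2.8%. Power is Φ(2.24) = 98.7% unadjusted and Φ(2.47) = 99.3% adjusted.

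| Assumed R² | True size of 5% test | Half-width unadjusted (min) | Half-width adjusted (min) | Excess width | Power unadjusted | Power adjusted |
|---|---|---|---|---|---|---|
| 0% | 5.0% | 14.8 | 14.8 | 0% | 97.7% | 97.7% |
| 10% | 3.9% | 14.8 | 14.1 | 5.4% | 98.3% | 98.7% |
| 20% | 2.8% | 14.8 | 13.3 | 11.8% | 98.7% | 99.3% |
| 30% | 1.9% | 14.8 | 12.4 | 19.5% | 99.2% | 99.7% |

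**Simulation check** (300 patients, 4,000 runs per setting, normal data, minimisation with an assumed 80:20 coin). Null rejection at R² of 0, 10, 20 and 30%:
- t-test: 5.2, 3.8, 3.0 and 2.0%.
- Wilcoxon: 4.8, 3.7, 3.1 and 2.1%.
- Linear model with the four factors: 5.0 to 5.6%.

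Allocation in pairs within the 16 cells gave the same pattern for the t-test (5.0, 3.7, 2.9, 2.7%).

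**Check of the proposed methods** (5,000 null runs per setting; normal, skewed and ordinal data). With 300 patients, null rejection was 4.6 to 5.4% for the linear model with robust standard errors and 4.4 to 5.6% for rank ANCOVA. With 150 patients it was 4.6 to 5.6% and 4.6 to 5.7%. The 150-patient check used the nominal 5% level, not the O'Brien-Fleming interim bound.

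**The 15-minute recording grid.** Rounding the primary outcome up to this grid left the result unchanged. The mean half-width was 14.9 min unadjusted against 15.0, 14.2, 13.4 and 12.5 adjusted. Coverage was 95.4, 96.0, 97.5 and 98.0% unadjusted, and 94.8 to 95.6% adjusted.

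**The case against.** **The plan is valid as written.** Unadjusted tests after balanced allocation do not exceed their nominal error rate, and the Randomization section never claims that the factors predict outcome. No statement in the documents is contradicted. This stands, and it is why the point concerns efficiency only. A reader might infer that the mismatch biases the comparison or inflates the false-positive rate; the direction is the opposite. A reader might also take the sentence on baseline comparisons as ruling out adjustment; it concerns testing for baseline differences and is silent on adjustment.

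**Every non-zero figure rests on an assumed R².** This stands. At R² = 0 there is no gain.

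**The small power change depends on about 98% power at 150 per group, which conflicts with the plan's stated 80%.** This partly stands. Test size and proportional excess width do not depend on the number of patients, but the power columns do. At 75 per group, where power is 80.0% with R² = 0, an R² of 20% would give 82.6% unadjusted and 87.9% adjusted. With the planned 150 per group, the gain is under 1 point.

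**Gains for secondary outcomes cannot be sized.** This stands. A reader might infer a gain of around 10 points in power. Such figures need an effect size and a scale that the plan does not give. For skewed data with a log-SD of 0.8 and an R² of 30%, an effect of 0.32 SD on the log scale gave 81% for Wilcoxon and 89% for rank ANCOVA. Taking 0.32 of the raw SD as a shift gave about 100% for both.

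**Withdrawals after randomisation weaken the balance.** This is true but minor: random loss of 10% moves the size at R² = 20% from 2.8% to about 3.0%.

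**Adjustment adds work and can complicate reporting.** This stands as a cost and is the reason to keep the change narrow.

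**Conclusion.** The point holds as a low-cost improvement. Allocation uses four factors that the planned analysis ignores. If they predict an outcome, the planned tests are conservative and the 95% intervals too wide; if they do not, adjustment costs essentially nothing in precision.

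For the primary outcome the gain is modest. The half-width falls by 0.7 min at R² = 10% and by 2.4 min at R² = 30%, with almost no change in power. Whether that counts as small depends on R²: at 20 to 30% the interval would be about 12 to 20% too wide.

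The mismatch and the direction of its effect are certain. The size is not: it rests on the assumed R², close balance on the factors, the stated SD, and 150 analysed patients per group.

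**What to change.** In the Analysis section, prespecify procedure, gender, age group (≥70) and BMI group (≥32) as main-effect covariates in the primary analysis and in the continuous and ordinal secondary analyses, at both interim and final. Leave the existing rule for choosing between t-test and Wilcoxon, and the alpha-spending approach, as they are.

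- **Where a t-test is planned:** a linear model of the outcome on arm plus the four factors, with robust standard errors, reporting the adjusted mean difference and its 95% interval.
- **Where Wilcoxon is planned:** rank ANCOVA. Rank the outcome over both arms, regress the ranks on arm plus the four factors, and test arm. Keep the descriptive interval beside it, labelled unadjusted.
- **Binary and nominal outcomes:** keep the planned chi-square and Fisher tests.
- **Sensitivity analyses:** report the planned unadjusted t and Wilcoxon tests.

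**Cost.** A few lines of SAP text and code. The allocation already needs all four factors, so no new data or patients are required. The drawbacks are a little more analysis work and, for rank-based outcomes, an adjusted P value beside an unadjusted interval; the two can occasionally disagree. The choice should be fixed before any unblinded look, so that adjustment cannot be chosen by its result.

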#### Sample Size

An a priori power analysis was conducted using internal data from Mayo patients undergoing primary TJA with mepivacaine (N=6) and low-dose bupivacaine (N=5). In these two cohorts, standard deviations of the time to return of full lower extremity motor function were 37 minutes and 89 minutes, respectively, yielding a pooled estimate of the common standard deviation equal to 65.6 minutes. Assuming that similar variability will be observed in the proposed study, a sample of 150 subjects per group (300 total) will be required to have 80% power to detect a difference of at least 30 minutes in mean time to return to full lower extremity motor function between the 2 study groups. With the typical volume of the participating surgical group, we anticipate enrollment will be complete within 3 months.

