Bupivacaine has been shown to have the lowest incidence of TNS and is currently the most widely used medication for spinal anesthesia. While advantageous for avoiding TNS, bupivacaine has a slow onset time coupled a long duration of action, which can delay postoperative recovery. Low-dose bupivacaine (10 mg) regimens are increasingly used; however, issues remain with the unpredictable temporal profile. Mepivacaine (70 mg) is a shorter acting local anesthetic compared to bupivacaine with a more predictable duration of action, raising interest as an alternative for procedures such as TKA and THA with consistent performance times.

In this randomized controlled trial, mepivacaine will be compared to low dose bupivacaine spinal anesthetics. The primary outcome will be time from spinal insertion to return of motor function. Secondary outcomes will evaluate pain scores, opioid consumption, urinary retention, transient neurologic symptoms, length of PACU

stay, length of hospital stay, time to participation in physical therapy and walking distance with physical therapy.

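### The trial is sized on a difference in means, but the rank-sum fallback stops measuring that difference if spreads are as unequal as in the pilot and recovery times are right-skewed

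*Combined protocol and SAP*

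**What the plan says.** The Sample Size section reports that, in the mepivacaine and low-dose bupivacaine pilot cohorts (6 and 5 patients), the "standard deviations of the time to return of full lower extremity motor function were 37 minutes and 89 minutes, respectively". It combines these, "yielding a pooled estimate of the common standard deviation equal to 65.6 minutes", and expects similar variability in the trial. The target is "to detect a difference of at least 30 minutes in mean time to return to full lower extremity motor function", and the section concludes that "a sample of 150 subjects per group (300 total) will be required to have 80% power".

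The Analysis section compares continuous outcomes, the primary one included, by "two-sample t-tests if the data are sufficiently normally distributed; otherwise non-parametric Wilcoxon rank sum tests will be used". It gives no criterion for normality, does not say whether the t-test pools the variances, and does not mention unequal spread. No power is given for the rank-sum test.

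The Background, under Research Question and Aims, gives a reason to expect different spreads. For low-dose bupivacaine it says that "issues remain with the unpredictable temporal profile", and it describes mepivacaine as the more predictable drug.

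**The concern.** The rank-sum test asks whether times in one arm tend to exceed times in the other. That matches a difference in means when the two distributions have the same shape and differ only in location. If one arm is both more spread out and skewed, its mean is pulled away from its typical value by more than in the other arm, and the two questions can have different answers.

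The plan brings these conditions together. It is sized on a mean, its pilot SDs differ by a factor of 2.4, and it moves to the rank-sum test only when the data do not look normal. At stake is whether the primary p-value speaks to the 30-minute effect for which the trial is sized, and whether the planned power applies to the test actually used.

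**Working it through.** **Inputs from the documents.** SDs 37 and 89 minutes, pilot sizes 6 and 5, planning SD 65.6, difference 30 minutes, 150 per group (Sample Size); two-sided 5% level (Analysis); 1:1 allocation (Study Design and Methods).

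**Assumptions.** The shapes of the distributions and a bupivacaine mean of 150-300 minutes. The interim look is ignored.

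**1. The plan's own figures.**
- Pooled SD = √[(5×37² + 4×89²)/9] = √(38,529/9) = 65.4. The stated 65.6 is within the rounding of the two SDs (65.0-65.9).
- n per group = 2 × (1.960 + 0.842)² × 65.6² / 30² = 75.1, so about 76. The stated 150 per group is not reproduced; about 150 is the total.
- Power at 150 per group with SD 65.6: the standard error is 65.6 × √(2/150) = 7.57, 30/7.57 = 3.96, and Φ(3.96 − 1.96) gives 97.7%.

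**2. A comparison of means with the pilot SDs.** The standard error is √[(37² + 89²)/150] = √61.9 = 7.87, 30/7.87 = 3.81, and Φ(3.81 − 1.96) gives 96.8%. With equal arms, unequal spread costs a mean-based test very little.

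**3. How firm the inequality is.** F = 89²/37² = 5.79 on 4 and 5 degrees of freedom, two-sided p = 0.08. Assuming normality, the 95% interval for the SD ratio is about 0.9 to 7.4, which includes 1.

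**4. Simulation of the fallback.** 150 per group, SDs 37 and 89, two-sided 5% tests, 3,000 trials per right-skewed case. The middle column is the share of trials that significantly favour *mepivacaine slower* (nominally 2.5%). The last column is the share that detect a true 30-minute gain.

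| Shape assumed for times | Equal means: mepivacaine slower | Power, 30-minute gain |
|---|---|---|
| Gamma, bupivacaine mean 150 / 200 / 250 / 300 | 44 / 29 / 20 / 16% | 62 / 73 / 77 / 83% |
| Lognormal, bupivacaine mean 150 / 200 / 250 / 300 | 66 / 49 / 34 / 26% | 60 / 66 / 71 / 76% |
| Shifted gamma, skewness 0.5 / 0.75 / 1.0 / 1.5 | 13 / 22 / 34 / 63% | 86 / 79 / 70 / 51% |

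In the same right-skewed cases, Welch has about 5% two-sided error and 97-98% power. Rounding times up to the 15-minute recording grid changes nothing material.

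**5. Which condition does the work.**
- Unequal SDs with normal times: about 6% rank-sum rejection at equal means, split evenly by direction, and about 95% power.
- Common SD 65.6 with skewness 1: about 5% error and 99% power.
- Unequal SDs with skewness −1: the bias reverses. *Mepivacaine faster* is declared in 34% of equal-mean trials, and power exceeds 99%.

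The problem therefore needs unequal spread and skew together, and its direction follows the direction of the skew.

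**The case against.** The strongest reply is that the rank-sum test is not in error here. In the skewed equal-mean cases with a bupivacaine mean of 150-250, mepivacaine's median really is 9-17 minutes longer, and the probability that a mepivacaine patient takes longer than a bupivacaine patient is 0.54-0.58. The test detects a real difference in typical patients. The aims and endpoints speak only of time to return of function; the mean is named only in the sizing sentence. This stands: the issue is a mismatch between two target quantities, and choosing the mean is partly a judgement.

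Four stronger readings are tempting, and the documents do not support them:
- *Unequal SDs alone break the fallback.* They do not, as the normal case shows. Skew is also needed, and the documents give no shape, means or medians.
- *The trial could report the wrong sign.* The high rates of *mepivacaine slower* arise when the means are equal, so there is no sign of a mean difference to reverse. With a true 30-minute gain, *slower* appeared in at most 0.03% of trials across the eight gamma and lognormal cases.
- *The plan commits to a pooled-variance t-test.* It says only that the t-test is two-sample, which includes Welch. The common SD belongs to the power calculation.
- *Power necessarily falls below 80%.* It is 86% at skewness 0.5, and 83% for gamma times with a bupivacaine mean of 300.

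It is also fair to say that 6 and 5 patients are weak evidence of unequal spread. That favours a method that is valid whether or not the spreads differ.

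**Conclusion.** The point holds conditionally. If spreads differ as in the pilot and times are right-skewed, the fallback does not measure the mean difference on which the trial is sized. Over the right-skewed cases tabulated, it favours *mepivacaine slower* in about 13-66% of equal-mean trials and has about 51-86% power for a 30-minute mean gain. In the shifted-gamma cases, power drops below 80% from skewness of about 0.75. Welch is not affected in this way.

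Right skew is plausible for a duration bounded at zero, but it is not documented, and neither is the range of means. With normal times little is lost. The change is worth making because it costs almost nothing and protects against a case that the plan's own pilot figures make credible. It does not show that the trial would reach a false conclusion.

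**What to change.** In the Analysis section, make the primary comparison the difference in mean time to full motor function, with its 95% confidence interval, from an unequal-variance (Welch) t-test, whatever a normality check shows. Report the rank-sum test as a supportive analysis, described as a comparison of which arm tends to have longer times.

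The cost is a change of wording. If spreads turn out equal, Welch loses essentially nothing at 150 per group. The one small drawback is that a mean is more sensitive to a few very long times, which the supportive rank-sum result would help to show.

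Replacing 65.6 by the equal-weight SD, √[(37² + 89²)/2] = 68.2, is not worth doing alone. Any edit to the Sample Size section should also restate the power: SD 65.6 and a 30-minute difference need about 76 per group for 80%, and 150 per group gives about 97%.

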### Subject Information

*Target accrual is the proposed total number of subjects to be included in this study at Mayo Clinic. A "Subject" may include medical records, images, or specimens generated at Mayo Clinic and/or received from external sources.*

Target accrual: 300 patients

Subject population (children, adults, groups): Adult males and females

Inclusion Criteria:

1. Unilateral primary TKA or THA
2. 18+ years of age
3. Able to provide informed consent

Exclusion Criteria:

1. Body mass index (BMI) > 45 kg/m^2
2. Severe drug allergy\* to medications used in this study, including non-steroidal anti-inflammatory drugs (i.e. celecoxib and ketorolac), and local anesthetics.
  - *\*defined as an immune reaction resulting in shortness of breath, hives, anaphylaxis, wheezing, and fever*
  -
3. Contraindication to spinal anesthesia technique (e.g., known spinal stenosis, coagulopathy, sepsis, infection at site of injection, uncooperative, refusal, anticoagulation medications not held within appropriate time frame\*).
  - *\*Per ASRA guidelines, Clopidogrel (Plavix) held for at least 7 days, Dabigatran (Pradexa) held for at least 5 days, Rivaroxaban (Xarelto) held for at least 3 days, Warfarin (Coumadin) held for at least 5 days or recent INR of less than 1.4, Enoxaparin (Lovenox) with doses > 1 mg/kg held for close to 24 hours.*
4. Known to be currently pregnant or actively breastfeeding++
  - *++ Patients that have a previous history of menopause, hysterectomy, or tubal ligation will not be required to perform a pregnancy test. Female patients that do not meet this criterion will be asked to submit a urine sample, and will require a negative urine sample in order to proceed with study protocol. Urine sample be collected pre-procedurally.*
5. Impaired cognition
6. Lower extremity motor deficit

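### The plan calls 150 per group necessary for 80% power, but its own inputs need 76 to 77 per group, and 150 per group gives 97.7%

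*Combined protocol and SAP*

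**What the plan says.** The Sample Size section bases its calculation on internal data from 11 patients, 6 given mepivacaine and 5 given low-dose bupivacaine. It reports that the "standard deviations of the time to return of full lower extremity motor function were 37 minutes and 89 minutes, respectively". One planning value is then used for both arms, with the two figures described as "yielding a pooled estimate of the common standard deviation equal to 65.6 minutes". The section assumes that the trial will show similar variability and concludes that "a sample of 150 subjects per group (300 total) will be required to have 80% power to detect a difference". The target effect is "a difference of at least 30 minutes in mean time to return to full lower extremity motor function".

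The Analysis section supplies the rest. It states "All statistical tests will be two-sided", sets the significance level at 0.05, and compares continuous outcomes by two-sample t-test, with the Wilcoxon rank sum test if the data are not sufficiently normal. It also plans one interim analysis with O'Brien-Fleming type spending. Randomization and Blinding gives 1:1 allocation. Subject Information carries the number forward: "Target accrual: 300 patients".

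**The concern.** A difference of 30 minutes against an SD of 65.6 is a standardised effect of about 0.46. An effect of that size does not normally call for 150 per group at 80% power, so the stated requirement looked about twice too large.

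This matters because the power statement is the only justification the plan gives for 300 patients. If it is wrong, there are two possibilities. Either about 150 more patients would be randomised than the stated target needs, or the larger size was intended for a reason the plan does not give. In both cases a reader of the protocol is misinformed about the power and about the smallest effect the trial can reliably detect.

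**Working it through.** **Inputs.** Difference 30 min, SD 65.6 min, power 80% (Sample Size); two-sided alpha 0.05, two-sample t-test (Analysis); 1:1 allocation (Randomization and Blinding). No outside figure is needed.

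**Pooled SD.** √[(5 × 37² + 4 × 89²)/9] = 65.4. The plan has 65.6. Rounding of the two SDs can explain the difference, and it does not affect the result. I use 65.6.

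**Sample size for 80% power.**
n per group = 2 × (1.95996 + 0.84162)² × (65.6/30)² = 2 × 7.849 × 4.7815 = 75.06, rounded up to 76.
With the exact noncentral t, 76 per group gives 79.98% and 77 gives 80.5%, so 77. The total is 152 to 154. The plan's 150 per group is not reproduced.

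**Power at 150 per group.**
Standard error = 65.6 × √(2/150) = 7.575 min.
30/7.575 = 3.960, and Φ(3.960 − 1.960) = 0.977. The noncentral t also gives 97.7%.

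**What 150 per group does deliver at 80% power.**
- Detectable difference: 2.8016 × 7.575 = 21.2 min (exact t: 21.3).
- SD at which 30 min has 80% power: 30/(2.8016 × √(2/150)) = 92.7 min (exact t: 92.4). This exceeds even the larger pilot SD of 89.

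**Could another reading give 150 per group?** Per-group sizes are for 30 min and 80% power unless noted; they use the normal approximation except where a t value is shown.

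| Reading | n per group |
|---|---|
| One-sided test | 60 |
| Unequal SDs 37 and 89: (37² + 89²) × 7.849/30² = 81.02 | 82 |
| SD 89 in both groups (contradicts the stated 65.6) | 139 (t: 140) |
| Wilcoxon, relative efficiency 0.955 | 79 to 80 |
| Wilcoxon, worst-case efficiency 0.864 | 87 to 88 |
| O'Brien-Fleming interim, inflation about 1% | about 77 |
| 90% power | 101 |
| 95% power | 125 |

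None gives 150. At a final alpha of 0.049 to allow for the interim analysis, power at 150 per group is still about 97.6%. For withdrawals to explain the gap, the loss would have to be 1 − 76/150 = 49% (also 49% from 77).

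**Possible origin.** 150 in total, that is 75 per group, gives 79.97% power by the normal approximation and 79.5% by the t-test. A total may therefore have been entered as a per-group number. This is an inference, and the error stands without it.

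**The case against.** The arithmetic is hard to dispute. The serious objections concern how much it matters and what to do about it.

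- **The error is in the safe direction.** On its own inputs the trial has more power than it claims. The type I error rate, the estimate and the test are unaffected. The template text under Data Analysis also says that power analyses are not required for minimal risk research. All of this is true. It limits the harm, but a calculation was given, it is wrong, and the accrual target has no other stated support.

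- **A margin may be wise.** The SD rests on 9 degrees of freedom. Assuming normality and a common variance, the 95% interval around 65.6 runs from about 45 to 120 min, so the 92 min at which 150 per group gives 80% power is well inside it. If the SD were 89 in both groups, 77 per group would give about 55% power and 150 about 83%. This is a good argument for keeping 300 and against a simple cut to 154. It does not rescue the sentence, which assumes variability like the pilot's and claims no margin.

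- **Separate powering for TKA and THA.** About 75 per group within each procedure would also lead to 300. However, the plan uses procedure only as a stratification factor and states a single pooled primary comparison.

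- **The interim analysis.** It should not be argued that the trial has its 80% power at the halfway look. At the O'Brien-Fleming type boundary for half the information (two-sided about 0.003), 75 per group has about 42% power for 30 min. The look may also come before half enrolment, because it is triggered by 2 months or half enrolment, whichever is first.

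**Conclusion.** The concern holds. On the plan's stated inputs, 80% power for 30 minutes needs 76 to 77 per group, not 150. The stated total of 300 is 95% to 97% above the 152 to 154 required (300/154 = 1.95; 300/152 = 1.97). At 150 per group the power is 97.7%, or equivalently 80% for a difference of about 21 minutes.

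The conclusion rests on the SD of 65.6, two-sided alpha 0.05, 1:1 allocation and a t-test. Allowing for unequal SDs, the Wilcoxon fallback or the interim analysis, each taken singly, moves the requirement to 88 per group at most. The fault lies in the justification and reporting of the sample size, not in the validity of the primary comparison. It should be corrected because it concerns the primary endpoint and is nearly twofold.

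**What to change.** **Preferred: keep 300 and correct the sentence.** For example: with 150 patients per group, an SD of 65.6 minutes and a two-sided 5% test, the trial has about 97% power to detect a 30-minute difference in means; this corresponds to 80% power for about 21 minutes, or for 30 minutes if the SD is as large as about 92 minutes. Then give the reason for the margin, such as the uncertainty of an SD from 11 patients, day-of-surgery withdrawals, or precision for secondary outcomes if that was the intention. This costs one or two sentences and changes nothing in conduct.

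**Alternative: size the trial for 80% power as stated.** Give 76 to 77 per group (about 154 in total), add an explicit withdrawal allowance, and change the target accrual in Subject Information to match. This saves up to about 146 patients (300 − 154) before that allowance, but it should not be adopted without addressing the weak SD estimate: at an SD of 89 in both groups, power would fall to about 55%.

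If 300 was meant to power TKA and THA separately, say so and add those comparisons to the Endpoints and Analysis sections.
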